Trumenba Meningococcal Group B Vaccine (Wyeth/Pfizer Pharmaceuticals). The vaccine is a suspension for intramuscular injection in 0.5 mL single-dose prefilled syringes. Each 0.5 mL dose contains 60 micrograms of each FHbp variant (total of 120 micrograms of protein), 0.018 mg of PS80 and 0.25 mg of Al³⁺ as AlPO₄ in 10 mM histidine buffered saline at pH 6.0. Trumenba is administered as a three dose series (0.5 mL each) according to a 0-, 2-, and 6-month schedule. Table 1 summarizes the various visits and procedures that will be performed during the 7-month study.

Table 1: Trumenba Meningococcal Group B vaccine study: Summary of visits and events (total of 13 subjects)

Activity	Day 0	2 months (60 to 80 day)	3 months (3-to 6 weeks Post Dose 2)	6 months	7 to 10 Days Post Dose 3	7 months (3 to 6 Weeks Post Dose 3)
Screen for inclusion and exclusion criteria	X	X		X		
Informed written consent	X				X (Review for obtaining optional blood sample)	
Targeted physical exam and medical history	X	X		X		
Blood draw	30 ml (Sample A)		75 ml (Sample B)		60 ml* (Sample D)	75 ml (Sample C)
Type of blood sample	Serum only		Serum only		*Anti-coagulated for PBMC)	Serum only
Immunization	X	X (Dose 2)		X (Dose 3)		
Collect information on SAE and severe reactions		X	X	X	X	X

Note, total volume of serum for all subjects having three blood samples is 180 ml; for those providing optional blood sample, 240 ml.

Blood specimens. Blood specimens will consist of 30 ml obtained immediately before immunization with dose 1, and 75 ml obtained three to six weeks after dose 2 and dose 3 (total of 3 blood draws, designated A, B, and C, in all 13 subjects). Sera will be separated and stored frozen for serologic assays. In consenting subjects, an additional 60 ml of anti-coagulated blood (Sample D) will be obtained 7 to 10 days after vaccine dose 3 for isolation of individual B cells for preparation of recombinant anti-FHbp Fabs (Aim 2).

Safety and immunization. On enrollment, subjects will undergo a brief history and directed physical exam. Subjects who meet all inclusion criteria and no exclusion criteria will receive an immunization at visit 1 (study day 0), visit 2 (2 months; range 40 to 80 days) and visit 4 (6 months, range 180 to 240 days). Visits 3 and 6 will consist of blood draws only at 3 to 6 weeks after doses 2 and 3, respectively. At each visit information will be obtained on notable adverse events occurring within 7 days of vaccination, and

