any serious adverse event (SAE) occurring during the 7-month study period. The FDA defines a SAE as “Death, life-threatening, or requiring hospitalization (not necessarily caused by the vaccine).

Immunologic assessment. Sera will be assayed by ELISA for titers of anti-FHbp antibodies and the ability of the antibodies to inhibit or enhance binding of FH to FHbp. Complement-mediated bactericidal activity will be measured with human complement using a panel of diverse strains. Other assays for meningococcal immunity may also be performed such as antibody binding to live bacteria measured by flow cytometry, and the ability of the serum antibodies to confer passive protection in an infant rat bacteremia model. All of these methods have been performed routinely in our laboratory for more than a decade (see for example, citations ^{1,2,18,19}). All of the assays using live meningococci will be performed in a BL2+ facility using protocols approved by the CHORI Institutional Biosafety Committee (IBC).

Data Safety Monitoring Plan

The study is slightly above minimal risk because the age group 26 to 55 years is considered currently “off-label” for use of an FDA-approved vaccine for the age group 10 to 25 years. No serious adverse events are anticipated related to vaccination. The other study procedures include three to four blood draws over seven months from healthy adults in which a total of less than 240 ml of blood will be obtained (approximately half of the volume that can be safely drawn at a single blood donation at the blood bank).

ADVERSE REACTIONS

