Clinical Trials Experience: (From the package insert). The safety of Trumenba was evaluated in 4,282 subjects 11 through 25 years of age in 7 clinical studies (4 randomized controlled and 3 supportive non-controlled studies) conducted in the US, Europe, and Australia. A total of 4,250 adolescents (11 through 18 years of age) and 32 adults (19 through 25 years of age) received at least one dose of Trumenba. A total of 1,004 subjects 11 through 25 years of age in the control groups received saline placebo and/or one of the following vaccines: Human Papillomavirus Quadrivalent (Types 6, 11, 16, and 18) Vaccine, Recombinant [HPV4]; a non-US licensed tetanus toxoid, reduced diphtheria toxoid, acellular pertussis and inactivated polio virus vaccine; or Tetanus Toxoid, Reduced Diphtheria Toxoid and Acellular Pertussis Vaccine Adsorbed (Sanofi Pasteur Ltd.). The safety evaluation in the 7 studies included an assessment of: (1) solicited local and systemic reactions, and (2) use of antipyretic medication after each vaccination

Solicited Local and Systemic Adverse Reactions: The Trumenba vaccine was generally well-tolerated although most patients (85-93%) experienced injection site reactions; fatigue (43-64%), headache (35-57%), muscle pain (31-42%), or chills (16-30%). These reactions were usually of mild to moderate severity and transient. In general the rates of these reactions were only slightly higher than those of subjects

receiving comparator control vaccines (including a U.S.-licensed quadrivalent human papilloma vaccine).

Serious Adverse Events: Among the 4 controlled studies (Trumenba N=2557, control N=1004), serious adverse events were reported in 44 (1.7%) subjects who received Trumenba and 16 (1.6%) control subjects, for individuals who received at least one dose.

Non-serious Adverse Events: Among the 4 controlled studies (Trumenba N=2557, control N=1004), AEs that occurred within 30 days of vaccination were reported in 739 (28.9%) subjects who received Trumenba and 313 (31.2%) subjects in the control group, for individuals who received at least one dose. AEs that occurred at a frequency of at least 2% and were more frequently observed in subjects who received Trumenba than subjects in the control group were injection site pain and headache.

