Blood specimens from living human subjects. The material will be obtained specifically for research purposes.

c) Recruitment plans:

Subjects will be recruited from hospital employees and from medical students. Potential volunteers will have the study explained to them verbally by the study coordinator, research nurse or physician. If they express interest, they will be given an “informed consent form.” which will inform them further about the purpose of this study, what is known about the vaccine that will be administered, and the blood sampling procedures that will be done should they decide to enroll in the study. The form also will contain information on the risks and benefits of participating. They will be asked to read

this form carefully and ask questions before deciding to enroll. Prospective volunteers may take as much time as they like to make up their minds. They will be informed that participation is voluntary. Should they decide not to participate, they will be informed that they may receive the vaccine outside the study by going to their physician or employee health.

d) Potential risks:

Vaccine-related risks include local reactions such as erythema, induration, pain at injection site, which occur in up to 50% of subjects. Systemic reactions such as fever, chills, malaise nausea, headache, fatigue, myalgia or arthralgia occur in approximately 90% of immunized persons. These side effects are usually of mild severity and last less than 1 or 2 days and are similar to side effects experience with most vaccines. Blood drawing may cause some discomfort, local bruising, and rarely, infection. Some donors may experience transient light-headedness. The total volume of blood obtained over the six months duration of this study (<200 ml) is less than taken on one occasion during routine donation of a unit of blood at a blood bank.

e) Protection against risks:

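### Do the conflicting local-reaction rates and blood totals in section VI.d (Potential risks) call for a change to the plan?

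*Combined protocol and SAP*

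**What the plan says.** Four places in the combined protocol and SAP bear on this.

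- **Section VI.d, Potential risks.** On local reactions: "Vaccine-related risks include local reactions such as erythema, induration, pain at injection site, which occur in up to 50% of subjects". On systemic reactions: "Systemic reactions such as fever, chills, malaise nausea, headache, fatigue, myalgia or arthralgia occur in approximately 90% of immunized persons". On blood: "The total volume of blood obtained over the six months duration of this study (<200 ml) is less than taken on one occasion".
- **Adverse Reactions, Solicited Local and Systemic Adverse Reactions.** The summary says that "most patients (85-93%) experienced injection site reactions; fatigue (43-64%), headache (35-57%), muscle pain (31-42%), or chills (16-30"%).
- **Section IV, Procedures, Table 1 and its note.** The three required samples total 180 ml; "for those providing optional blood sample, 240 ml".
- **Data Safety Monitoring Plan.** Over three to four draws in seven months, "a total of less than 240 ml of blood will be obtained", described as about half of one blood-bank donation.

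On what is done with safety data, the general study design in section IV restricts detailed collection to notable severe or serious events. The Safety paragraph of section V tabulates serious adverse events, severe local or systemic events, and early withdrawals.

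**The concern.** Section VI.d is the risk description in the human-subjects part of the protocol, so an ethics reviewer would be expected to read it. For local reactions it gives a ceiling of 50%, while another section of the same document starts its range at 85%. The discrepancy runs in the reassuring direction. The blood total also reads low, because VI.d makes no exception for the optional fourth sample, although section VI.e, directly after it, describes that sample.

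Three further details seem to point the same way. The systemic figure of about 90% exceeds every single-symptom rate in the Adverse Reactions section, as if the local and systemic figures had been exchanged. VI.d calls reactions usually mild where the other section says usually mild to moderate. VI.d also speaks of six months where Table 1 is introduced as covering a seven-month study.

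If VI.d were the yardstick for judging reactions in the off-label group aged 26 to 55, or the basis of the study's risk classification, a wrong figure there could mislead. That is what has to be checked.

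**Working it through.** **1. Blood volume.** Inputs are the draws in Table 1 and the Blood specimens paragraph: sample A 30 ml, samples B and C 75 ml each, optional sample D 60 ml.

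- Required draws: 30 + 75 + 75 = 180 ml. This reproduces the Table 1 note and is below 200 ml, so VI.d is right for a subject giving only the three required samples.
- With sample D: 180 + 60 = 240 ml. This also reproduces the Table 1 note. It exceeds the VI.d ceiling by 240 - 200 = 40 ml, or 40/200 = 20%.
- The Data Safety Monitoring Plan says less than 240 ml where the four-draw sum is exactly 240 ml. The slip is one of wording only.
- VI.d uses the volume to say that less is taken than at one donation. By the Data Safety Monitoring Plan, a volume of about 240 ml is roughly half a donation, so that statement survives for every subject.

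**2. Local reactions.** VI.d gives "local reactions such as erythema, induration, pain at injection site, which occur in up to 50% of subjects"; the Adverse Reactions section gives 85-93%.

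- Gap: 85 - 50 = 35 points at the low end and 93 - 50 = 43 points at the high end.
- Expected number among 13 subjects: at most 0.50 × 13 = 6.5 under VI.d, against 0.85 × 13 = 11.05 to 0.93 × 13 = 12.09 under the other section.

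These do not overlap. VI.d names injection-site pain and states 50% as an upper limit for the group, so reading it symptom by symptom does not reconcile them.

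**3. Systemic reactions.** VI.d gives one figure for a group of symptoms: "headache, fatigue, myalgia or arthralgia occur in approximately 90% of immunized persons". The Adverse Reactions section gives four symptoms separately. The proportion with at least one of the four lies between the largest single rate and the sum of the rates, capped at 100%.

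- Low ends of the ranges: at least 43%; sum 43 + 35 + 31 + 16 = 125%, capped at 100%.
- High ends: at least 64%; sum 64 + 57 + 42 + 30 = 193%, capped at 100%.

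A combined rate near 90% is therefore possible, and VI.d names further symptoms such as fever, nausea and arthralgia. There is no contradiction here. An exchange of the two figures does not fit well either: it would cap systemic reactions at 50%, below the upper figures for fatigue (64%) and headache (57%).

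**4. Does anything in the plan use these figures?**

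- Risk classification: the Data Safety Monitoring Plan places the study slightly above minimal risk because of off-label use at ages 26 to 55. It does not derive this from a reaction rate.
- Safety analysis: only serious or severe events and early withdrawals are tabulated. VI.d gives no rate of severe reactions, so it supplies no comparator for that table.
- Thresholds: no section defines an unexpected reaction or sets a rule by reference to VI.d.
- Sample size: the 13 subjects are a convenience sample, justified by what can practically be enrolled.

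None of the four depends on the VI.d figures.

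**The case for a change.** The strongest case for acting is that this is information about risk to participants, that two figures in VI.d err on the favourable side, and that correcting them costs only a wording change and a submission to the IRB, which the protocol already promises for changes in procedures. Donors of sample D are a planned subset, since Aim 2 depends on them. Anyone drafting from VI.d alone would carry forward a local-reaction ceiling at odds with the protocol's own summary, and a blood total too low for those donors.

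What stands is the discrepancy itself on both points, and the sense in reconciling the sections if the document is edited for another reason, with the reaction rates checked against the package insert in Appendix A.

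What does not stand is the inferred harm. The reader of VI.d has the same protocol, with 85-93% in the Adverse Reactions section, both blood totals under Table 1, and the package insert listed as an appendix. Section VI.e states the optional 60 ml draw immediately after VI.d, and Table 1 schedules a separate consent review for it. The consent form is not among the documents, so no error in what participants were told can be claimed. The mild versus mild-to-moderate contrast is weak, since both sections qualify it with usually. The six-month figure is loose wording that the exclusion criteria share. Finally, correcting everything would not make the stated risk uniformly worse: replacing about 90% by single-symptom ranges of 16-64% would read as more favourable.

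**Conclusion.** The two inconsistencies are confirmed: a 35- to 43-point gap in the local-reaction rate, and a blood ceiling exceeded by 40 ml (20%) for donors of the optional sample only. The claims that the systemic rate is wrong, that two figures were exchanged, and that VI.d serves as a benchmark for observed reactions are not supported by the documents.

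These are clerical slips in a descriptive section. The conflicting range and the correct volumes are already in the protocol, and no procedure, threshold, analysis or conclusion draws on VI.d. No change to the plan follows. This rests on two assumptions: that the draw volumes in Table 1 are those taken, and that participant materials, which cannot be seen here, were not built on VI.d alone. The documents do not settle which reaction rate is right; that would need the package insert.
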